### **3.3 Inclusion of Women and Minorities**

NIH policy requires that women and members of minority groups and their subpopulations be included in all NIH-supported biomedical and behavioral research projects involving NIH- defined clinical research unless a clear and compelling rationale and justification establishes to the satisfaction of the funding Institute & Center (IC) Director that inclusion is inappropriate with respect to the health of the subjects or the purpose of the research. Exclusion under other circumstances must be designated by the Director, NIH, upon the recommendation of an IC Director based on a compelling rationale and justification. Cost is not an acceptable reason for exclusion except when the study would duplicate data from other sources. Women of childbearing potential should not be routinely excluded from participation in clinical research. Please see <http://grants.nih.gov/grants/funding/phs398/phs398.pdf>.

## 4. REGISTRATION PROCEDURES

### 4.1 Investigator and Research Associate Registration with CTEP

Food and Drug Administration (FDA) regulations require IND sponsors to select qualified investigators. NCI policy requires all persons participating in any NCI-sponsored clinical trial to register and renew their registration annually. To register, all individuals must obtain a CTEP Identity and Access Management (IAM) account (<https://ctepcore.nci.nih.gov/iam>). In addition, persons with a registration type of Investigator (IVR), Non-Physician Investigator (NPIVR), or Associate Plus (AP) (i.e., clinical site staff requiring write access to OPEN or RAVE or acting as a primary site contact) must complete their annual registration using CTEP's web-based Registration and Credential Repository (RCR) (<https://ctepcore.nci.nih.gov/rcr>). Documentation requirements per registration type are outlined in the table below.

Documentation Required	IVR	NPIVR	AP	A
FDA Form 1572	✓	✓		
Financial Disclosure Form	✓	✓	✓	
NCI Biosketch (education, training, employment, license, and certification)	✓	✓	✓	
HSP/GCP training	✓	✓	✓	
Agent Shipment Form (if applicable)	✓			
CV (optional)	✓	✓	✓	

An active CTEP-IAM user account and appropriate RCR registration is required to access all CTEP websites and applications. Additional information can be found on the CTEP website at <https://ctep.cancer.gov/investigatorResources/default.htm>. For questions, please contact the RCR **Help Desk** by email at [[contact]](mailto:[contact]).

## 4.2 Site Registration

N/A

## 4.3 MSK Patient Registration Process

Confirm in the electronic medical record that the patient has received the Notice of Privacy Practice. This must be obtained before the eligibility confirmation and obtaining of the research informed consent.

Confirm eligibility as defined in the section entitled Patient Selection.

Obtain informed consent, by following procedures defined in section entitled [Informed Consent Procedures](#).

During the registration process registering individuals will be required to complete a protocol specific Eligibility Checklist. The individual signing the Eligibility Checklist is confirming whether or not the participant is eligible to enroll in the study. Study staff are responsible for ensuring all institutional requirements necessary to enroll a participant to the study have been completed. See related Clinical Research Policy and Procedure #401 (Protocol Patient Registration).

## 4.4 Informed Consent Procedures

Before protocol-specified procedures are carried out, consenting professionals will explain full details of the protocol and study procedures as well as the risks involved to participants prior to their inclusion in the study. Participants will also be informed that they are free to withdraw from the study at any time. All participants must sign an IRB/PB-approved consent form indicating their consent to participate. Only those individuals designated on the protocol title page as consenting professionals may obtain informed consent. This consent form meets the requirements of the Code of Federal Regulations and the Institutional Review Board/Privacy Board of this Center. The consent form will include the following:

1. The nature and objectives, potential risks and benefits of the intended study.
2. The length of study and the likely follow-up required.
3. Alternatives to the proposed study. (This will include available standard and investigational therapies. In addition, patients will be offered an option of supportive care for therapeutic studies.)
4. The name of the investigator(s) responsible for the protocol.
5. The right of the participant to accept or refuse study interventions/interactions and to withdraw from participation at any time.

Before any protocol-specific procedures can be carried out, the consenting professional will fully explain

the aspects of patient privacy concerning research specific information. In addition to signing the IRB Informed Consent, all patients must agree to the Research Authorization component of the informed consent form

Each participant and consenting professional will sign the consent form. The participant must receive a copy of the signed informed consent form.

#### 4.5 General Guidelines

Eligible patients will be entered on study centrally at Memorial Sloan Kettering Cancer Center by the Study Coordinator.

Following registration, patients should begin protocol treatment within 5-7 days. Issues that would cause treatment delays should be discussed with the Principal Investigator. If a patient does not receive protocol therapy following registration, the patient's registration on the study may be canceled. The Study Coordinator should be notified of cancellations as soon as possible.

### 5. TREATMENT PLAN

#### 5.1 Agent Administration

Treatment will be administered on an outpatient basis. Reported adverse events and potential risks are described in Section 7. Appropriate dose modifications are described in Section 6. No investigational or commercial agents or therapies other than those described below may be administered with the intent to treat the patient's malignancy.

Regimen Description					
Agent	Premedications; Precautions	Dose	Route	Schedule	Cycle Length
MLN0128 (TAK- 228)	none	3mg	oral	daily continuous	28 days (4 weeks)

Patients will be treated MLN0128 (TAK-228) 3mg oral daily continuously on an every 4 week schedule. MLN0128 (TAK-228) will be taken at the same time every day. The capsules should not be opened, chewed, or crushed. The patient will be given a medication diary at the beginning of each cycle of therapy. The medication diary, along with the pill bottles and any unused drug, will be returned to the clinic staff at the end of each cycle.

In cases where a subject misses dosing at his/her dosing time, the subject may still take the dose within 12 hours of the regular dosing time (subjects should not take 2 consecutive daily doses within 12 hours of each other). Subjects who vomit shortly after receiving MLN0128 (TAK-228) will not

receive a replacement dose. If confirmed that the study drug has been vomited, the dose should be noted as having been missed.

If severe emesis or mucositis prevents the patient from taking scheduled doses, that dose will be skipped. If emesis occurs after study medication ingestion, the dose will not be readministered, and patients should resume dosing at the next scheduled time with the prescribed dosage. Patients should record the occurrence of the emesis in their dosing diaries. Under no circumstance should a patient repeat a dose or double-up doses.

## 5.2 General Concomitant Medication and Supportive Care Guidelines

Multiple human metabolizing enzymes are involved in the Phase I metabolism of MLN0128 (TAK-228). When normalized for human liver content, the CYP isoforms CYP3A4, CYP2C9, and CYP2C19 appear to contribute to MLN0128 (TAK-228) metabolism. MLN0128 (TAK-228) displayed low potential ( $IC_{50} > 25 \mu M$ ) for inhibition of the major human CYP isoforms.

Strong CYP1A2 inhibitors and CYP inducers should be administered with caution, at the discretion of the investigator (see [Appendix F](#)). Alternative treatments, if available, should be considered.

Histamine H2 receptor antagonists may be allowed, if needed provided that the histamine H2 receptor antagonist is not taken within 12 hours before and within 6 hours after study drug administration. Patients receiving histamine H2 receptor antagonists before enrollment must stop using these medications for at least 24 hours before their first dose of study drug. Examples of histamine H2 receptor antagonists include ranitidine, famotidine, nizatidine, and cimetidine and nizatidine. Cimetidine, a moderate cytochrome P450 (CYP)1A2 inhibitor, is not recommended as a first choice H2 receptor antagonist.

Because there is a potential for interaction of MLN0128 (TAK-228) with other concomitantly administered drugs through the cytochrome P450 system, the case report form must capture the concurrent use of all other drugs, over-the-counter medications, or alternative therapies. The Principal Investigator should be alerted if the patient is taking any agent known to affect or with the potential to affect selected CYP450 isoenzymes.

### Management of Hyperglycemia

On the basis of the clinical experience in TAK-228 trials, most episodes of hyperglycemia observed occurred within the first 60 days after initiation of treatment with TAK-228 and have been either Grade 1 or Grade 2, and have responded quickly to oral metformin. Hyperglycemia has not been dose-limiting since the institution of a standard regimen for early treatment of hyperglycemia.

All patients developing hyperglycemia during the study should have their glucose closely monitored by study staff. The investigator may choose to continue close monitoring of patients who develop Grade 1 hyperglycemia (fasting glucose  $>ULN \leq 160$  mg/dL) or, alternatively, consider initiating treatment with an oral hypoglycemic agent, such as metformin. All patients with  $\geq$ Grade 2 hyperglycemia (fasting glucose  $>160$  mg/dL) must be treated aggressively with oral hypoglycemic agents and/or insulin as clinically

indicated. The investigator should consult an endocrinologist, if needed, to aid in optimizing the patient's hyperglycemia treatment plan.

It is recommended that patients with elevated fasting blood glucose be initially treated with a fast acting insulin sensitizer such as metformin at 500 mg orally QD, and titrate up to a maximum of 1000 mg orally BID as needed. Concurrent addition to metformin of DPP-4 inhibitors (eg, sitagliptin or vildagliptin) and/or insulin should also be considered. Oral sulfonylureas (eg, glipizide or glyburide) should be used with caution, due to the higher risk of inducing hypoglycemia in patients. The dose of oral hypoglycemic agents should be adjusted in patients with renal insufficiency. In addition, patients should be encouraged to follow a low carbohydrate diet once hyperglycemia is first observed.

If any fasting serum glucose reading performed at the site indicates hyperglycemia ( $>ULN$  or  $\geq 110$  mg/dL), the study staff should first confirm that the patient was fasting at the time of blood specimen collection (ie, nothing by mouth for at least 8 hours before collection).

### **In-Home Daily Fasting Glucose Monitoring**

In addition to obtaining fasting glucose levels at the clinic visits as outlined in the Schedule of Events, all patients will be given a prescription for a glucometer to monitor their daily FBG levels at home. The level should be collected daily, predose on dosing days, and at approximately the same time each day.

On Cycle 1 Day 1, the patient will be provided an in-home glucometer. Patients should be trained on proper use of the glucometer and instructed to collect a daily FBG level every morning (predose on dosing days), starting on Cycle 1 Day 2. Patients will be instructed to bring the glucometer with them to each study visit so that the data collected can be reviewed and recorded in the source documents.

Investigators will be responsible for reviewing the home glucose monitoring logs for hyperglycemia. The patient will be instructed to contact the site immediately if the value is abnormal (ie,  $\geq 150$  mg/dL) for further instructions on the management of their hyperglycemia. Hyperglycemia observed during home glucose monitoring should be confirmed in the clinic.

If no irregularities in the fasting blood glucose level are observed during a minimum of 2 consecutive months, then the frequency of in-home fasting blood glucose testing can be reduced to a minimum frequency of once weekly, depending on the investigator's judgment and approval. Patients will continue to notify the investigator of fasting blood glucose levels that exceed 150 mg/dL and, if blood glucose levels are not well controlled, or if the patient requires either oral hypoglycemic agents or insulin to control blood glucose levels, then the frequency of in-home testing of FBG levels will be reinstated to daily.

### **5.3 Duration of Therapy**

In the absence of treatment delays due to adverse event(s), treatment may continue until one of the following criteria applies:

- Disease progression (at the discretion of the PI, patients who continue to derive clinical benefit

may be treated beyond progression; see [Section 5.3.1](#) for details),

- Intercurrent illness that prevents further administration of treatment,
- Unacceptable adverse event(s),
- Patient decides to withdraw from the study, or
- General or specific changes in the patient's condition render the patient unacceptable for further treatment in the judgment of the investigator.

### 5.3.1 Treatment Beyond Progression

Patients can be treated beyond progression at the discretion of the PI for clinical benefit and will undergo scans per the usual schedule. In these instances, the scan demonstrating RECIST PD will be used as a new baseline to determine further progression. Patients will be removed from the study if RECIST PD is achieved relative to the new baseline scan unless otherwise discussed with the Principal Investigator, if there is intolerable toxicity or if the patient withdraws consent.

## 5.4 Duration of Follow Up

Patients will be followed for 4 weeks after removal from study or until death, whichever occurs first. Patients removed from study for unacceptable adverse event(s) will be followed until resolution or stabilization of the adverse event.

## 5.5 Criteria for Removal from Study

Patients will be removed from study when any of the criteria listed in Section 5.4 applies. If a patient is removed for any reason other than disease progression, he or she will be replaced. The reason for study removal and the date the patient was removed must be documented in the Case Report Form. Patients can, at the discretion of the PI, receive treatment beyond progression for clinical benefit (see [section 5.3.1](#) for details).

## 6. DOSING DELAYS/DOSE MODIFICATIONS

Toxicities will be graded using the NCI CTCAE Version 4.0 and dose modifications of the study drugs will be made for hematologic and other toxicities. Patients experiencing study drug related toxicities that require a delay in dosing for >21 days will be discontinued from further participation in this study. In the event that patients must have treatment delayed with a treatment cycle due to toxicities, those doses held during a cycle will not be made up.

Dose Level	MLN0128 (TAK-228) Dose
0	3 mg flat dose daily continuous
-1	2 mg flat dose daily continuous
-2	2 mg daily 5 days/ week
-3	1 mg 5 days/week
-4	Withdraw from study

Treatment Modification for MLN0128 (TAK-228)-Related Adverse Events		
Event	CTCAE. V4 Grade	Action to be Taken
QTc prolongation	≥ Grade 3 or > 60ms change from baseline on at least two separate ECGs	
First Occurrence:
 
 
• Omit MLN0128 (TAK-228) dose
 
• Perform an analysis of potassium and magnesium, and if below lower limit of normal, correct with supplements to within normal limits. Concomitant medication usage must be reviewed.
 
• Perform a repeat ECG within one hour of the first QTcF of 500 ms
 
• If QTcF remains > 500 ms, repeat ECG as clinically indicated, but at least once a day until the QTcF returns to < 480 ms. Seek cardiologist input
 
• Once QTcF prolongation has resolved, MLN0128 (TAK-228) may be restarted at a one lower dose level
 
 
Second Occurrence:
 
 
• Permanently discontinue patient from the study treatment
 

	Other Cardiac Events	Grade 1-2
	Grade 3	
Omit dose of MLN0128 (TAK-228) until resolved to ≤ Grade 1
 
 
• If resolved within 7 days, then resume at same dose level of MLN0128 (TAK-228).
 
• If resolved in >7 days, resume at ↓1 dose level of MLN0128 (TAK-228).
 
• If not resolved in 21 days, then discontinue patient from study treatment.
 

	Grade 4	Permanently discontinue patient from the study treatment
Treatment Modification for MLN0128 (TAK-228)-Related Adverse Events		
Event	CTCAE. V4 Grade	Action to be Taken
ENDOCRINE		
Fasting Plasma Glucose (FPG) (2 hrs fasting)	Grade 1	
Maintain dose level of MLN0128 (TAK-228), check FPG every week
 
 
• Initiate or intensify with appropriate anti-diabetic treatment as per investigator's discretion
 
• Instruct patient to follow dietary guidelines according to local and/or institutional standards for management of diabetes mellitus (such as those provided by the American Diabetes Association) during the study
 
• Consider use of oral anti-hyperglycemic therapy such as metformin
 
 
Check FPG daily for 8 weeks, then continue checking at least every 1 week

Grade 2	
First Occurrence:
 
 
• If signs or symptoms of hyperglycemia (for example, mental status changes, excessive thirst, polyuria), omit dose of MLN0128 (TAK-228) immediately and manage as for Grade 3 hyperglycemia (below)
 
• If asymptomatic, maintain MLN0128 (TAK-228) dose and re-check FPG within 24 hours. If grade worsens or improves then follow specific grade recommendations: 
 
○ If FPG remains at Grade 2: 
 
▪ Maintain dose level of MLN0128 (TAK-228)
 
▪ Initiate or intensify with appropriate anti-diabetic treatment
 
▪ Instruct patient to follow dietary guidelines according to local and/or institutional standards for management of diabetes mellitus (such as those provided by the American Diabetes Association) during the study
 
▪ Consider use of oral anti-hyperglycemic therapy such as metformin
 
 
 
○ If FPG does not resolve to <math>\leq</math> Grade 1 within 7 days after initiation/intensifying anti-diabetic treatment: 
 
▪ Omit dose of MLN0128 (TAK-228) if
 
 
 
 
 

---------	--

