**Treatment Modification for MLN0128 (TAK-228)-Related Adverse Events**

Event	CTCAE. V4 Grade	Action to be Taken
		
not already done
 
 
▪ Monitor FPG at least weekly until FPG resolves to <math>\leq</math> Grade 1
 
▪ Then re-start MLN0128 (TAK-228) and <math>\downarrow</math>1 dose level
 
▪ Continue with anti-diabetic treatment
 
▪ Check FPG weekly for 8 weeks, then continue checking every 2 weeks
 
 
Second and Subsequent Occurrence:
 
 
• Maintain dose level of MLN0128 (TAK-228), re- check FPG within 24 hours. If grade worsens or improves then follow specific grade recommendations. If FPG remains at Grade 2: 
 
○ Omit dose of MLN0128 (TAK-228)
 
○ Initiate or intensify with appropriate anti-diabetic treatment
 
○ Monitor FPG at least twice weekly until FPG resolves to <math>\leq</math> Grade 1
 
○ Then re-start MLN0128 (TAK-228) and <math>\downarrow</math>1 dose level
 
○ Continue with anti-diabetic treatment
 
○ Check FPG at least weekly for 8 weeks, then continue checking at least every 2 weeks
 
 
 

	Grade 3	
Immediately omit MLN0128 (TAK-228), initiate or intensify medication with appropriate anti-diabetic treatment, re-check FPG within 24 hours. If grade worsens or improves then follow specific grade recommendations.
 
 
• If FPG remains at Grade 3: 
 
○ Administer intravenous hydration and intervention for electrolyte/ketoacidosis/hyperosmolar disturbances as clinically appropriate
 
○ Continue to omit dose of MLN0128 (TAK-228)
 
○ Monitor FPG at least twice weekly until FPG resolves to <math>\leq</math> Grade 1
 
○ If FPG resolves to <math>\leq</math> Grade 1 in 7 days or less, then re-start MLN0128 (TAK-228) at the same dose level
 
 
 
• If FPG remains greater than Grade 1 severity for
 

--	---------	--

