**Treatment Modification for MLN0128 (TAK-228)-Related Adverse Events**

Event	CTCAE. V4 Grade	Action to be Taken
		
more than 7 days, then discontinue patient from study treatment:
 
 
○ Initiate or continue anti-diabetic treatment as appropriate
 
○ Instruct patient to follow dietary guidelines according to local and/or institutional standards for management of diabetes mellitus (such as those provided by the American Diabetes Association) during the study
 
○ Consider use of oral anti-hyperglycemic therapy such as metformin
 
○ Check FPG at least weekly for 8 weeks, then continue checking at least every 2 weeks
 
 
For non-fasting plasma glucose >250-500mg/dL (> 13.9 – 27.8 mmol/L) accompanied by signs/symptoms of hyperglycemia (for example, mental status changes, excessive thirst, polyuria), or presence of blood or urine ketones, omit MLN0128 (TAK-228) and follow guidance for management of Grade 3 fasting plasma glucose (FPG).

	Grade 4	
Immediately omit dose of MLN0128 (TAK-228), initiate or intensify medication with appropriate anti-diabetic treatment, re-check within 24 hours, if confirmed Grade 4:
 

• Administer intravenous hydration and intervention for electrolyte/ketoacidosis/hyperosmolar disturbances as clinically appropriate

• Discontinue patient from the study. Instruct patient to follow dietary guidelines according to local and/or institutional standards for management of diabetes mellitus (such as those provided by the American Diabetes Association) during the study

• Consider use of oral anti-hyperglycemic therapy such as metformin

• Check FPG weekly for 8 weeks, then continue checking at least every 2 weeks if clinically indicated

--	---------	---

Treatment Modification for MLN0128 (TAK-228)-Related Adverse Events		
Event	CTCAE. V4 Grade	Action to be Taken
		For non-fasting plasma glucose >500 mg/dL (> 27.8 mmol/L) accompanied by signs/symptoms of hyperglycemia (for example, mental status changes, excessive thirst, polyuria), or presence of blood or urine ketones, discontinue MLN0128 (TAK-228) and following guidance for management of Grade 4 fasting plasma glucose (FPG).
GASTROINTESTINAL		
Mucositis oral	Grade 1	Maintain MLN0128 (TAK-228) dose level

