### Directions:

- You will need to perform the glucose monitoring test on a daily basis, predose on dosing days, and at approximately the same time each day- prior to breakfast. **You are required to fast for at least 8 hours prior to testing.** Fasting means not eating or drinking any liquids (with the exception of water).
- In the log, please write in the date, note the time you completed the glucose test, whether you fasted or not (fed state) before the test, and your glucose levels as provided by your glucometer.
- Please contact the site immediately if the value is abnormal (ie,  $\geq 150$  mg/dL) for further instructions on the management of their hyperglycemia. Hyperglycemia observed during home glucose monitoring should be confirmed in the clinic.

Site Contact Name: \_\_\_\_\_

Site Contact: Number: \_\_\_\_\_

Day	Date	Approximate time of Test (Circle AM or PM)	Fasting or Fed (Circle One)	Glucose Test Results (mg/dL)
Day 1		____ : ____ am / pm	Fasting or Fed	
Day 2		____ : ____ am / pm	Fasting or Fed	
Day 3		____ : ____ am / pm	Fasting or Fed	
Day 4		____ : ____ am / pm	Fasting or Fed	
Day 5		____ : ____ am / pm	Fasting or Fed	

Day 6		____:____ am / pm	Fasting or Fed	
Day 7		____:____ am / pm	Fasting or Fed	
Day 8		____:____ am / pm	Fasting or Fed	
Day 9		____:____ am / pm	Fasting or Fed	
Day 10		____:____ am / pm	Fasting or Fed	
Day 11		____:____ am / pm	Fasting or Fed	
Day 12		____:____ am / pm	Fasting or Fed	
Day 13		____:____ am / pm	Fasting or Fed	
Day 14		____:____ am / pm	Fasting or Fed	
Day 15		____:____ am / pm	Fasting or Fed	
Day 16		____:____ am / pm	Fasting or Fed	
Day 17		____:____ am / pm	Fasting or Fed	
Day 18		____:____ am / pm	Fasting or Fed	
Day 19		____:____ am / pm	Fasting or Fed	
Day 20		____:____ am / pm	Fasting or Fed	
Day 21		____:____ am / pm	Fasting or Fed	
Day 22		____:____ am / pm	Fasting or Fed	
Day 23		____:____ am / pm	Fasting or Fed	
Day 24		____:____ am / pm	Fasting or Fed	
Day 25		____:____ am / pm	Fasting or Fed	
Day 26		____:____ am / pm	Fasting or Fed	
Day 27		____:____ am / pm	Fasting or Fed	
Day 28		____:____ am / pm	Fasting or Fed	

Patient Signature: \_\_\_\_\_ Date: \_\_\_\_\_

Investigator Signature: \_\_\_\_\_ Date: \_\_\_\_\_

**APPENDIX F      LIST OF RELEVANT CYTOCHROME P450 INHIBITORS  
AND INDUCERS**

---

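### Section 6 conflicts with Section 5.2 and Appendix E on what counts as a fasting glucose sample (2 hours against at least 8), and with its own 21-day rule on how long a Grade 2 pneumonitis hold may last (4 weeks).

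*Combined protocol and SAP*

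**What the plan says.** **Glucose.** The endocrine rows in Section 6 are headed "Fasting Plasma Glucose (FPG) (2 hrs fasting". Section 5.2 (Management of Hyperglycemia) says that after a high fasting reading at the site "the study staff should first confirm that the patient was fasting at the time of blood specimen collection", and explains this as "nothing by mouth for at least 8 hours before collection". The Appendix E home log tells patients: "You are required to fast for at least 8 hours prior to testing". Exclusion 3.2.9 and the study calendar call for a fasting glucose without giving hours. Section 6 also has separate rules for non-fasting glucose. In the band above 250 and up to 500 mg/dL the drug is withheld when the value is "accompanied by signs/symptoms of hyperglycemia (for example, mental status changes, excessive thirst, polyuria), or presence of blood or urine ketones, omit MLN0128 (TAK-228"). Above 500 mg/dL a parallel rule stops the drug.

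**Pneumonitis.** The opening paragraph of Section 6 discontinues any patient whose drug-related toxicity needs a dosing delay of more than 21 days. The Grade 2 non-infectious pneumonitis row withholds the drug until Grade 1 or better, restarts one level lower, and stops the drug only if the patient has not recovered by 4 weeks. The Grade 3 pneumonitis row prints no time limit.

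**The concern.** These rows decide whether a patient is held, reduced or taken off drug, so two investigators following the same text should reach the same action.

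For glucose, the fasting definition selects the rule. A value graded under the fasting rows can trigger a hold at Grade 3, or a hold and a lower restart level at persistent or recurrent Grade 2. The same value classed as non-fasting triggers nothing in the table unless it exceeds 250 mg/dL with symptoms or ketones. Section 5.2 tells staff to check the fast but does not say what follows if it was shorter than 8 hours.

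For pneumonitis, the reading chosen decides whether a patient stays on treatment. It also decides replacement, because Section 5.5 replaces anyone removed for a reason other than progression.

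**Working it through.** The plan states no figure to reproduce. The check sets the passages side by side and needs only simple arithmetic.

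**1. Fasting window.** Section 6 heading: 2 h. Section 5.2 and Appendix E: at least 8 h. 8 − 2 = 6, so the definitions disagree for samples taken from 2 to under 8 hours after food.

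| Sample in that window | Read by the Section 6 heading | Read by Section 5.2 |
|---|---|---|
| Grade 3 value | "Immediately omit MLN0128 (TAK-228), initiate or intensify medication with appropriate anti-diabetic treatment, re-check FPG within 24 hours" | Non-fasting: table acts only above 250 mg/dL with symptoms or ketones |
| First Grade 2 value, no symptoms | "If asymptomatic, maintain MLN0128 (TAK-228) dose and re-check FPG within 24 hours" | As above |
| Grade 2 not resolved after 7 days of anti-diabetic treatment | Hold, then restart one level lower | As above |
| Recurrent Grade 2, still Grade 2 on re-check | Hold, then restart one level lower | As above |

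The two readings therefore differ mainly in holds and in the reductions that follow them.

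**2. Pneumonitis window.** 4 weeks × 7 = 28 days, and 28 − 21 = 7 days. Both limits are counted from the first held dose, which is an assumption. Because the drug is withheld until recovery, recovery time is in effect the dosing delay. A patient who recovers on days 22 to 28 is discontinued under the opening paragraph and restarted one level lower under the row.

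**3. Is the 4-week limit part of a pattern?** Section 6 rows that print a recovery limit before discontinuation:

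- 21 days, 9 rows, all Grade 3: other cardiac events, oral mucositis, fatigue, neutropenia, bilirubin, AST/ALT, creatinine, rash, other adverse events.
- 7 days, 3 rows, all Grade 3: fasting glucose, febrile neutropenia, thrombocytopenia.
- 4 weeks, 1 row: Grade 2 pneumonitis.

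9 + 3 + 1 = 13 rows. Only the pneumonitis row exceeds 21 days. If it is an intended exception, Grade 2 gets a longer hold than Grade 3, which only the 21-day sentence covers.

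**4. Consequence per pneumonitis patient.** The 21-day reading means one discontinuation and, under Section 5.5, one replacement. Section 13.2 expects 1 patient per arm every 2 months, so one replacement takes about 2 months in an open cohort.

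**5. How often.** The adverse event list in Section 7.1.1 places pneumonitis in its under-3% category (390 patients, no split by grade). If that ceiling held here (an assumption), 0.03 × 40 = 1.2, so fewer than 1.2 of the 40 planned patients would have pneumonitis of any grade. Among the 20 extension patients (10 each in cohorts 1 and 2), 0.03 × 20 = 0.6. Grade 2 cases recovering on days 22 to 28 would be only a part of these. The documents give no basis for counting glucose samples in the 2-to-under-8-hour window.

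**The case against.** The best reply on glucose is that the passages telling people how to obtain a fasting sample agree on 8 hours, and that the 2 hours is one parenthesis in a row heading. Section 5.2 puts the fasting check first, and "Hyperglycemia observed during home glucose monitoring should be confirmed in the clinic". The Grade 2 to 4 rows also call for a re-check within 24 hours. This narrows the problem considerably. It does not remove it, because the Grade 3 hold comes before its re-check, and the re-check falls under the same 2-hour heading.

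On pneumonitis, a specific row may be read as overriding a general sentence. That is a fair reading, but no visible text says so. The table's closing note on nausea and vomiting and part of the eligibility list are cut off in the text available, so the absence of an exception can be asserted only for what is shown.

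The conflict may never arise in practice, as the under-3% figure suggests. Section 13.3.2 keeps all eligible patients in the response analysis, with the possible exception of those never dosed, so replacement does not drop anyone from it. The accrual cost cannot apply to cohort 3, which is closed, and a patient restarted under the 4-week reading might later be removed and replaced anyway. All of this stands, and it limits the size of the point. The calendar and exclusion 3.2.9 contradict nothing; adding hours there is harmonisation only.

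**Conclusion.** Both contradictions hold and should be fixed. The fasting definitions disagree over a 6-hour window, and the pneumonitis limits over 7 days of a hold if both run from the first held dose. In each case, following the text as written gives different instructions on holding, reducing or stopping treatment. Few pneumonitis patients are expected, and the number of glucose samples is unknown. The claim concerns consistent conduct; it does not extend to the response endpoint, the two-stage boundaries, type I error or power. Which fasting time or hold limit is clinically right is not judged here.

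**What to change.** Reconcile the passages, with the clinical team choosing the values:

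1. Use one fasting definition in Section 5.2, the Section 6 glucose rows and Appendix E, and carry it into the study calendar and exclusion 3.2.9. State which Section 6 rows apply to a sample that does not meet it.
2. Give one maximum hold for Grade 2 pneumonitis in both the opening text of Section 6 and the row, or write the exception into the opening text explicitly.

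The cost is wording in the next amendment, with no added visits, procedures or patients.
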